### **4.4 Medical/Surgical History and Procedures/Non-Drug Therapies**

The presence/absence of any current medical condition and/or other significant medical/surgical history will be coded using Medical Dictionary for Regulatory Activities (MedDRA) Version 20.0. Any procedures/non-drug therapies will also be coded using MedDRA or World Health Organization (WHO) Drug Enhanced Dictionary Version March 2017 B2, as appropriate.

Medical/surgical history will be summarized by treatment, and listed by subject.

Procedures/non-drug therapies will be summarized by treatment, and listed by subject.

### **4.5 Prior and Concomitant Medications**

Concomitant medication is defined as any medication other than the trial product that is taken on or after the first dose of rivaroxaban (i.e., stop date is missing or is after the date of the first dose of rivaroxaban). Details of all medications must be recorded at trial entry. Any changes in concomitant medications must be recorded at each visit. The information collected for each concomitant medication includes dosage, route, start date, stop date (or continuing) and indication. Prior medications will be recorded at the screening visit and will be defined as those medications with start and end date prior to first dose of rivaroxaban. Concomitant medications will be defined as those medications with a stop date after the first dose of study drug or with a missing stop date. Prior and concomitant medications will be coded using the World Health Organization (WHO) Drug Enhanced Dictionary (March 2017 B2).

Prior and concomitant medications will be summarized by treatment including Anatomical Therapeutic Chemical (ATC) classification, preferred term and reported term. Medications will also be listed by subject.

### **4.6 Pharmacokinetic Analysis**

#### **4.6.1 Plasma and Serum Concentrations**

Blood samples for PK assessment of ciraparantag and its metabolite BAP, and rivaroxaban, will be analyzed using Liquid Chromatography/Mass Spectrometry (LC/MS) assay methodology. Blood samples will be analyzed by the Bioanalytical Services department of [REDACTED] to obtain serum concentrations of ciraparantag and its metabolite, and plasma concentrations of rivaroxaban. Serum and plasma concentrations will be listed at each time point by subject, and summarized by treatment at each time point using descriptive statistics (n, mean, SD, geometric mean, coefficient of variation (CV%), median, min and max values). Values below the quantification limit (BQL) will be treated as “0” in the summary statistics. Descriptive statistics that are not quantifiable will be designated as ‘NC’ in the summaries and a footnote added, NC = not calculable.

Plots of mean concentration levels of ciraparantag and its metabolite, and rivaroxaban versus time will be generated for each treatment. Plots of individual subject’s concentration levels of ciraparantag and its metabolite, and rivaroxaban versus time will also be generated.

#### 4.6.2 Pharmacokinetic Parameters

PK calculations will be performed based on actual time of blood sample collection, using noncompartmental methods, using Phoenix WinNonlin (Version 6.3 or higher, [REDACTED] [REDACTED]). Values of BQL are set to 0 if they occur prior to the first or after the last quantifiable concentration, and are set to missing for data points in between.

PK parameters for ciraparantag (PER977) and BAP, as displayed in [Table 2](#). PK parameters for rivaroxaban will include  $C_{max}$ ,  $T_{max}$ ,  $AUC_{(0-24)}$ ,  $AUC_{(0-last)}$ ,  $t_{1/2}$ ,  $K_{el}$ ,  $CL/F$  and  $V_z/F$ , if data allow. These PK parameters will be listed by subject and summarized by treatment using descriptive statistics (n, mean, geometric mean, median, and inter-quartile range (Q1:Q3), SD, CV%, min, and max).  $T_{max}$  and  $t_{last}$  will be described using n, min, 25th-percentile, median, 75th percentile, and max. The start time for rivaroxaban PK analysis is after rivaroxaban dosing.

**Table 2 Parameters for Serum Ciraparantag (PER977) and BAP**

Parameter	Units	Description
$C_{max}$	ng/mL	Maximum concentration in the sampled matrix, obtained directly from the observed concentration versus time data
$C_{24}$	ng/mL	Observed quantifiable analyte concentration in the sampled matrix at the 24-hour time point
$C_{last}$	ng/mL	Last observed quantifiable analyte concentration in the sampled matrix
$t_{last}$	h	Time of $C_{last}$ , obtained directly from the observed concentration versus time data

$T_{max}$	h	Time of $C_{max}$ , obtained directly from the observed concentration versus time data
$AUC_{(0-last)}$	ng·h/mL	The area under the concentration-time curve, from time zero to the last quantifiable concentration ( $C_{last}$ )
$AUC_{(0-inf)}$	ng·h/mL	Area under the concentration-time curve in the sampled matrix from zero (pre-dose) extrapolated to infinite time by addition of the last quantifiable concentration divided by the elimination rate constant: $AUC_{(0-last)} + C_{last}/\lambda_z$
$\lambda_z$	1/h	Apparent terminal rate constant
$t_{1/2}$	h	Apparent terminal half-life, determined as $\ln(2)/\lambda_z$
CL	L/h	Systemic clearance after IV dosing, calculated for PER977 only
$V_z$	L	Volume of distribution after IV dosing, calculated for PER977 only
$V_{ss}$	L	Steady-state volume of distribution after IV dosing, calculated for PER977 only
$MR_{Cmax}$		Metabolite to parent (BAP/PER977) ratio of $C_{max}$
$MR_{AUC(0-last)}$		Metabolite to parent (BAP/PER977) ratio of $AUC_{(0-last)}$
$MR_{AUC(0-inf)}$		Metabolite to parent (BAP/PER977) ratio of $AUC_{(0-inf)}$

The  $MR_{Cmax}$ ,  $MR_{AUC(0-last)}$ , and  $MR_{AUC(0-inf)}$  are molecular weight corrected molar ratios of metabolite/parent.

The following PK parameters for ciraparantag (PER977) and its metabolite, BAP, will be calculated for diagnostic purposes and listed, but will not be summarized.

**Table 3 Listing Parameters for Serum Ciraparantag (PER977) and BAP**

$T_{1/2}$ , Interval	The time interval (h) of the log-linear regression to determine $t_{1/2}$
$t_{1/2}$ , N	Number of data points included in the log-linear regression analysis
Rsq	Goodness-of-fit statistic for calculation of $\lambda_z$ (regression coefficient)
$\%AUC_{ex}$	Percentage of $AUC_{(0-inf)}$ that is extrapolated from $t_{last}$ to infinity, calculated as: $100 \times [1 - (AUC_{last}/AUC_{0-inf})]$ , where $t_{last}$ is the time of the last measurable plasma drug concentration

#### 4.6.3 Dose Proportionality

The dose proportionality of exposure PK parameters for PER977 and BAP ( $AUC_{(0-inf)}$ ,  $AUC_{(0-last)}$ , and  $C_{max}$ ), over the administered dose range will be investigated using the following power model:

$$\log(\text{PK parameter}) = a + b * \log(\text{dose})$$

where log is the natural log (LN)

Dose proportionality will be assessed statistically using the above power model approach with the logarithm of PK parameters as the dependent variables and the logarithm of the dose as the independent variable for subjects who receive one dose at a given dose interval. The intercept (a) and the slope (b) together with their 90% CI will be estimated and summarized for each PK parameter. Parameters 'a' and 'b' will be estimated using an ordinary least-squares approach or the equivalent. Dose proportionality will be declared if the 90% CI for the slope parameter 'b' lies entirely within the critical region (0.80, 1.25).

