1.2.4 PER977-02-001

PER977-02-001 was a randomized single-blind sequential group ascending ciraparantag reversal dose study in healthy volunteers who received a single dose of 60 mg edoxaban in the morning on Days 1-4 followed on Day 3 and Day 4 by a single IV dose of study drug. Five dose cohorts of 15 mg, 30 mg, 60 mg, 180 mg, and 360 mg ciraparantag (25 mg, 50 mg, 100 mg, 300 mg, and 600 mg ciraparantag acetate), respectively were planned and completed. Any subject who did not have a minimum increase in WBCT of 25% above baseline at the pre-study drug time point on Day 3 was discontinued from the study and replaced.

The pharmacokinetic results show that following 10-minute IV injection of ciraparantag on Day 3 and Day 4, serum PER977 C_{max} were typically observed at 0.25 hour (i.e., at the first postdose time point measured five minutes after the end of the 10-minute injection). Ciraparantag was then rapidly eliminated, with mean half-life ($t_{1/2}$) ranging from 0.207 to 0.336 hour (12.4 to 20.2 minutes). Clearance and volumes of distribution remained relatively constant across most doses and on both Days 3 and 4. Over the 24-fold dose range from 15 mg to 360 mg, ciraparantag C_{max} and total exposures ($AUC_{(0-inf)}$ and $AUC_{(0-last)}$) increased approximately proportionally to the dose increase. However, the

90% confidence interval (CI) of the slope for Day 4 AUC_(0-last) were completely above the predefined (0.9298, 1.0702) critical region; and the upper bounds of the 90% CI of the slopes for other exposure parameters on Day 3 and Day 4 were just above the upper limit of the critical region. Dose-proportionality thus could not be statistically concluded.

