3.2 Dose Rationale

A total of four dosing cohorts (Cohorts 1-4) are planned. The planned doses of ciraparantag or placebo (administered as a volume equivalent of ciraparantag) have been evaluated as single and repeat IV doses from 5 mg ciraparantag acetate (3 mg ciraparantag) up to 600 mg ciraparantag acetate (360 mg ciraparantag) in previous protocols (PER977-01-001, PER977-01-002, PER977-01-003, and PER977-02-001). All doses of study drug will be administered by IV injection over a minimum of 10 minutes.

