5.9 Dose Escalation/De-Escalation

Review of pharmacodynamic, AEs, clinical laboratory tests, and ECG data will be conducted by a group that includes the Principal Investigator, Medical Monitor(s), and representative(s) of the Sponsor. The group will be responsible for the decision to expand a given dose cohort, escalate (or de-escalate) to a different dose from the planned dose, or stop the study. All meetings will be documented with minutes.

The goal of the study is to explore the dose range of ciraparantag that reverses the anticoagulation induced by therapeutic doses of rivaroxaban at steady state. The study is intended to establish a dose of ciraparantag that fully reverses steady-state rivaroxaban, to evaluate at least one dose above the reversal dose to establish a therapeutic index, and at least one partial or no effect dose.

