9.6 Dose Proportionality

The dose proportionality of exposure PK parameters for PER977 and BAP (AUC_(0-inf), AUC_(0-last), and C_{max}), over the administered dose range will be investigated using the following power model:

$$\log(\text{PK parameter}) = a + b * \log(\text{dose})$$

where 'a' is the intercept and 'b' is the slope.

Dose proportionality will be assessed graphically and statistically using the above power model approach with the logarithm of PK parameters as the dependent variables and the logarithm of the dose as the independent variable for subjects who receive one dose at a given dose interval. The intercept (a) and the slope (b) together with their 90% CI will be estimated and presented for each PK parameter. Parameters 'a' and 'b' will be estimated using an ordinary least-squares approach or the equivalent. Dose proportionality will be declared if the 90% CI for the slope parameter 'b' lies entirely within the critical region (0.7968, 1.203) using the maximal dose ratio I = 3 (highest dose/lowest dose), a lower equivalence limit of 0.80, and an upper equivalence limit of 1.25.

Additionally, the geometric means for the primary PK parameters between adjacent dose levels will be compared using an analysis of covariance (ANCOVA) model including dose, gender and weight as fixed effects for subjects who receive one administration at a given dose interval. Geometric mean ratios for adjacent administrations (higher

dose/lower dose) and corresponding 90% CI will be presented. PER977 and BAP exposure parameters (C_{max} , $AUC_{(0-inf)}$, and $AUC_{(0-last)}$) will be plotted versus dose on linear and log-log scales for subjects who receive one administration at a given dose level using a scatterplot with individual exposures, regression line and corresponding confidence bands.

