### **2.2 Secondary Objectives**

The secondary objectives of this study are:

[figure not shown]
- To evaluate the safety and tolerability of ciraparantag 60 mg, 120 mg, 180 mg, and 30 mg, and additional cohorts if necessary, administered 4 hours after 20 mg rivaroxaban administration at steady state.
- To assess the PK characteristics of rivaroxaban and ciraparantag and its primary metabolite, 1,4-bis(3-aminopropyl) piperazine (BAP).

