#### **4.11 Changes from Pre-Specified Analyses**

The definition of concomitant medication is changed from “any medication other than the trial product that is taken during the trial including the screening period” in the protocol to “any medication other than the trial product that is taken on or after the first dose of rivaroxaban” in the analysis planned for this study.

In the statistical analysis of complete reversal, Tukey HSD multiple comparison procedure was replaced by one-tailed Dunnett’s test for comparison of treatment and placebo means.

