### Revision history

Version	Date	Comments
0.1 (Draft)	22 May 2017	First draft
0.2 (Draft)	06 June 2017	Updated based on internal review
0.3 (Draft)	20 June 2017	Updated based on sponsor's comments
0.4 (Draft)	27 June 2017	Updated based on protocol amendments
1.0 (Final)	28 June 2017	Finalized
2.0 (Final)	28 August 2017	Updated per protocol amendment (Version 4)
3.0 (Final)	06 March 2018	Updated per protocol amendment (Version 5)
4.0 (Final)	12 December 2019	Updated per protocol amendment (Version 6) and updates per SAP for PER977-02-011.
4.0 (Final)	06 February 2020	Updated per comments following review.
	12 March 2020	Updated per comments following review.
	20 March 2020	Updated per comments from PK consultant for sponsor, PK Director (████) and Biostatistics Director (████) regarding removing dose-proportionality ANCOVA statistical analysis and adding clarification for Rivaroxaban PK parameters and statistical analysis.

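### SAP 4.6.3 puts the 0.80–1.25 exposure limits directly on the power-model slope, and protocol 9.6 converts them with a dose ratio of 3 although the listed doses span 6-fold

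*SAP*

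**What the plan says.** Both documents fit log exposure (AUC(0-inf), AUC(0-last), Cmax) on log dose by least squares and look at the 90% confidence interval for the slope b. They differ in the region that the interval must fall inside.

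- Protocol 9.6 uses the "critical region (0.7968, 1.203) using the maximal dose ratio I = 3 (highest dose/lowest dose), a lower equivalence limit of 0.80" and an upper limit of 1.25.
- SAP 4.6.3 states: "Dose proportionality will be declared if the 90% CI for the slope parameter 'b' lies entirely within the critical region (0.80, 1.25"). It gives no dose ratio.
- Protocol 1.2.4, on the earlier edoxaban study with a 24-fold dose range (15 to 360 mg), reports an interval that was "completely above the predefined (0.9298, 1.0702) critical region".

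On doses, the SAP objective reads "To evaluate the safety and tolerability of ciraparantag 60 mg, 120 mg, 180 mg, and 30 mg", and protocol 3.2 says "A total of four dosing cohorts (Cohorts 1-4) are planned". Protocol 5.9 gives a review group the "decision to expand a given dose cohort, escalate (or de-escalate) to a different dose from the planned dose".

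On changes from the protocol, SAP 4.11 lists a new definition of concomitant medication and that "Tukey HSD multiple comparison procedure was replaced by one-tailed" Dunnett's test. The slope region is not there. On dose proportionality, the last revision-history entry mentions only "removing dose-proportionality ANCOVA statistical analysis"; its other item concerns rivaroxaban PK.

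**The concern.** The slope of a log-log model is not an exposure ratio. If exposure is proportional to dose to the power b, dose-normalised exposure changes by the factor r^(b−1) between the lowest and highest dose, where r is the ratio of those doses. Limits of 0.80 and 1.25 on that factor become limits on b only after conversion, and they narrow as the dose range widens. Placed unconverted on b, the same figures set a different and, over 30 to 180 mg, much looser standard.

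The PK of ciraparantag and BAP is a stated objective: primary in the protocol synopsis, secondary in the SAP. Since the SAP dropped the ANCOVA and the graphical assessment from this section, the slope rule is the only formal criterion left. The upper side matters most. Protocol 1.2.4 reports BAP slopes 12% to 48.3% above unity in the earlier study. That study covered a different range, so it shows relevance and does not predict the result here.

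**Working it through.** **Inputs.** Exposure limits 0.80 and 1.25, and r = 3 (protocol 9.6). Region (0.80, 1.25) on b (SAP 4.6.3). Doses 30, 60, 120 and 180 mg (protocol 2, SAP 2.2), so r = 180/30 = 6. Sixteen subjects per cohort at 3:1, hence 12 active per dose (SAP 3). The documents give no between-subject CV, so 20, 25, 30 and 40% are assumed.

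**1. Reproduce the sponsor's own regions.** Lower limit = 1 + ln(0.80)/ln(r); upper limit = 1 + ln(1.25)/ln(r).

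- r = 3: 1 ∓ 0.2231/1.0986 = (0.7969, 1.2031), matching protocol 9.6 to within 0.0001.
- r = 24: 1 ∓ 0.2231/3.1781 = (0.9298, 1.0702), matching the earlier study exactly.

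**2. Look for an r that gives the SAP region.** The lower limit 0.80 needs r = exp(0.2231/0.20) = 3.05. The upper limit 1.25 needs r = exp(0.2231/0.25) = 2.44. No single ratio gives both.

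**3. Apply the formula to the listed doses.** r = 6: 1 ∓ 0.2231/1.7918 = (0.8755, 1.1245).

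**4. Translate slopes into exposure ratios over 6-fold, as 6^(b−1).**

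- SAP limits: 6^(−0.20) = 0.70 and 6^(0.25) = 1.57.
- Protocol limits: 0.695 and 1.439.
- Even at r = 3, the SAP's upper limit means 3^(0.25) = 1.316.

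For example, a 90% CI of (1.13, 1.24) passes the SAP rule, fails the protocol's printed region and lies wholly above the 6-fold region.

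**5. Chance of declaring proportionality.** Error SD = sqrt(ln(1 + CV²)). With 12 subjects at each of four doses, the sum of squares of ln dose is 22.39 on 46 df. The slope SE is error SD/sqrt(22.39) = 0.042, 0.052, 0.062 and 0.081. Each cell comes from 400,000 simulations requiring the 90% t-interval to lie inside the region. Entries are % at CV 20/25/30/40.

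| True slope (ratio over 6-fold) | SAP (0.80, 1.25) | Protocol, r = 3 | r = 6 |
|---|---|---|---|
| 1.00 (1.00) | 100/98/93/70 | 100/97/89/58 | 80/53/26/2 |
| 1.1245 (1.25) | 91/77/64/44 | 58/44/35/23 | 5/5/4/0.5 |
| 1.15 (1.31) | 76/60/48/33 | 35/26/21/15 | 2 or less |
| 1.2031 (1.44) | 29/23/18/14 | 5/5/5/5 | under 1 |
| 1.25 (1.57) | 5/5/5/5 | about 1 or less | under 1 |

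On the lower side, slope 0.8755 (ratio 0.80) passes the SAP rule in 55% of trials at CV 20%, falling to 23% at CV 40%. The protocol's printed region is no stricter there.

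**6. If only 60, 120 and 180 mg are given.** Then r = 3, the sum of squares is 7.41 on 34 df, and the protocol region is correct. At slope 1.203 (ratio 1.25) the SAP rule declares proportionality in 16/12/9/2%.

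**The case against.** The arithmetic is not in dispute; attribution and weight are.

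- **The r = 6 region is printed nowhere.** Against the printed (0.7968, 1.203), the SAP is slightly stricter below and looser only above. This stands as a point of attribution. The lower-side error comes from the protocol's ratio of 3, and the 91% to 44% at slope 1.1245 combines both faults. The SAP's own share shows best at the protocol's upper limit of 1.203, where it passes 29% to 14% of trials against 5%.
- **The dose range is not settled.** The review group may depart from planned doses, extra cohorts are allowed, and the schema figure is not available. That also stands, and it is why r should come from the doses given. It does not rescue the SAP region, which matches no single r.
- **The change may have been deliberate.** The SAP was revised after comments from PK specialists, and the protocol delegates analysis detail to the SAP. That is possible, but no reason is given, 4.11 does not list the change, and the new limits are exactly the unconverted exposure limits.
- **Little depends on the label.** The slope and its interval are reported whatever is declared. This limits the severity; the stated rule is still wrong.

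**Conclusion.** The concern holds. SAP 4.6.3 applies exposure limits to a slope without conversion, and protocol 9.6 converts with a ratio that does not match its listed doses. If 30 to 180 mg are given, true slopes between 1.1245 and 1.25, or between 0.80 and 0.8755, breach the sponsor's 0.80–1.25 exposure criterion yet can be declared proportional. At the upper edge of that criterion the chance is 91% to 44% for CVs of 20% to 40%. Slopes of 1.25 or more, or 0.80 or less, still fail in about 95% of trials or more.

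The probabilities rest on the assumed CVs, constant error variance on the log scale and 12 complete active subjects at each dose. The regions and exposure ratios need only the dose range. The damage is confined to the proportionality declaration: the WBCT analysis, dose decisions and the reported slope with its interval are untouched. It should be fixed, but it does not threaten the trial.

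**What to change.** In SAP 4.6.3 and protocol 9.6, define the critical region as 1 + ln(0.80)/ln(r) to 1 + ln(1.25)/ln(r), where r is the highest dose actually given divided by the lowest. This yields (0.8755, 1.1245) for 30–180 mg and (0.797, 1.203) for 60–180 mg. List the change in SAP 4.11. Add that an interval not contained in the region means proportionality was not shown, and that the slope and 90% CI are reported either way.

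The work is a wording change and one line of code. The price is fewer declarations when PK is truly proportional: over 30–180 mg, 80/53/26/2% at CV 20/25/30/40%, against 100/98/93/70% under the current SAP rule. At high CV the declaration says little, and the slope with its interval should carry the conclusion.

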## 4.7 Efficacy Analyses

### 4.7.1 Primary Analysis

The efficacy endpoint will be PD assessment of clotting time by WBCT, efficacy endpoint will be summarized at observed time points and change and/or ratio from baseline values using descriptive statistics and graphical presentations. In addition, the summary by time point will include percent-of-baseline  $\leq 110\%$ ,  $\geq 125\%$ , and  $\geq 130\%$ . In addition, an additional summary of the counts and percentages of subjects with  $\leq 110\%$ , and  $\leq 115\%$  at each time point (categorical) will be produced.

Change-from-baseline and percent-of-baseline will be calculated for all efficacy endpoints. Baseline for all efficacy endpoints will be defined as the pre-rivaroxaban sample (approximately 4 hours before ciraparantag or placebo administration on Day 3).

The anticoagulant effect of rivaroxaban will be evaluated by comparing WBCT measured at pre-ciraparantag (about four hours post-rivaroxaban on Day 3) versus baseline (pre-rivaroxaban on Day 3). For the purposes of the efficacy analyses, subjects with percent-of-baseline WBCT at pre-ciraparantag  $< 125\%$  (i.e.,  $< 25\%$  increase) will be considered as rivaroxaban non-responders and excluded from all efficacy summaries and assessments.

Listings of individual efficacy variable collection times, as well as derived sampling time deviations (where applicable), will be provided.

Individual observed and baseline-adjusted values at scheduled time points and efficacy parameters will be listed and summarized by treatment. In addition, the nature of reversal of anticoagulation based on the definition of reversal of anticoagulation below using WBCT will be listed for each subject and summarized.

